4 STUDY DESIGN

4.1 Study Design

This is a Phase 3, open-label, randomized study to compare the efficacy and safety of defibrotide prophylaxis (DP) vs. best supportive care (BSC) in the prevention of hepatic veno-occlusive disease (VOD) as diagnosed using the modified Seattle criteria in adult and pediatric subjects undergoing hematopoietic stem cell transplant (HSCT) who are at high risk or very high risk of developing VOD. This study has an adaptive design with 1 interim analysis which has been detailed in a separate interim SAP.

A total of 400 subjects are planned for enrollment to ensure completion of approximately 360 subjects. An interim analysis overseen by an independent Data Monitoring Committee (DMC) is planned when 70% of subjects are evaluable for the primary efficacy endpoint (ie, VOD-free survival by Day +30 post-HSCT), with prespecified rules for efficacy stop, futility stop, and possible sample size re-estimation up to a maximum of 600 subjects total.

After informed consent or assent has been obtained from subjects, or legal parent/guardians or representatives, as applicable, screening procedures will be performed within 14 days of the scheduled start of the subject's HSCT conditioning regimen. Eligible subjects will be randomly assigned to receive defibrotide prophylaxis 25 mg/kg/day in addition to BSC (DP arm) or BSC alone (BSC arm) in a 1:1 ratio.

All subjects enrolled in the study will receive individualized standard of care therapy based on local institutional guidelines and subject need. This standard of care therapy or BSC is intended to serve as a study control for comparison with those subjects randomized to receive defibrotide prophylaxis. Subjects randomized to the BSC arm will receive standard of care therapy per institutional guidelines and subject need; subjects randomized to the defibrotide prophylaxis arm (DP arm) will also receive standard of care therapy based on local institutional guidelines and

subject need plus defibrotide prophylaxis. Prophylactic use of defibrotide added to BSC (DP arm) will be compared to BSC (BSC arm).

Administration of defibrotide to subjects in the DP arm will begin within 24 hours of the first dose of conditioning regimen, and will continue (for those subjects without a VOD diagnosis) for a recommended minimum of 21 days and end no later than Day +30 post-HSCT. For subjects in the BSC arm, administration of BSC according to institutional guidelines and subject need will begin on the first day of conditioning and continue until Day +30 post-HSCT or hospital discharge, whichever is sooner, or diagnosis of VOD, if applicable.

If subjects in either the DP or BSC arm develop VOD, per the modified Seattle criteria, they may receive rescue defibrotide treatment for VOD as prespecified in the informed consent and/or assent forms. For subjects in either arm who develop VOD, defibrotide for treatment of VOD should be administered until resolution of VOD or hospital discharge.

Subjects will continue to be monitored for development of late-onset VOD through Day +180 post-HSCT. Subjects who develop clinical signs and symptoms of VOD after hospital discharge/Day +30 post-HSCT will require more frequent monitoring (refer to specific instructions within schedule of assessments in the protocol), and re-admission to the hospital will be at the investigator's discretion.

An independent Endpoint Adjudication Committee (EPAC) blinded to study treatment assignment will be established to determine whether a subject meets the criteria for VOD by Day +30 post-HSCT and by Day +100 post-HSCT, using the modified Seattle criteria. The EPAC will review relevant electronic case report forms (eCRFs), results of diagnostic procedures, and ultrasound results; alternate etiology (eg, cholecystitis, viral hepatitis, acute graft-versus-host disease [GvHD]) will also be considered during review of subject data.

4.2 Study Objectives

4.2.1 Primary Objective

The primary objective of the study is to compare the efficacy of defibrotide prophylaxis in addition to BSC (DP arm) vs BSC alone (BSC arm) for the prevention of VOD as measured by VOD-free survival by Day +30 post-HSCT in subjects who are at high risk or very high risk for developing VOD.

4.2.2 Secondary Objectives

The key secondary objective of the study is to compare the efficacy of defibrotide prophylaxis in addition to BSC (DP arm) vs BSC alone (BSC arm) for the prevention of VOD as measured by VOD-free survival by Day +100 post-HSCT in subjects who are at high risk or very high risk for developing VOD.

Other secondary objectives of the study are as follows:

- To further compare the efficacy of defibrotide prophylaxis in addition to BSC (DP arm) vs BSC alone (BSC arm) on additional variables as follows:
 - Incidence of VOD by Day +30 post-HSCT
 - VOD-free survival by Day +180 post -HSCT
 - Non-relapse mortality (NRM) by Days +100 and +180 post-HSCT
 - Incidence of VOD-associated multi-organ dysfunction (MOD) (ie, severe VOD) by Days +30 and +100 post-HSCT (in those subjects who develop VOD)
 - Resolution of VOD by Day +180 post-HSCT and time to resolution of VOD (in those subjects who develop VOD)
 - Incidence of VOD after Day +30 post-HSCT up to Days +100 and +180 post-HSCT
- To compare the health-related quality of life using the following questionnaires:
 - 5-Level EuroQol-5D (EQ-5D-5L) (adults only)
 - EuroQol-5D for Youth (EQ-5D-Y), proxy version 1 (pediatric subjects 4 to 7 years of age)
 - EQ-5D-Y, self-report version 1 (pediatric subjects 8 to <16 years of age)
- To characterize the pharmacokinetics of defibrotide
- To compare the overall safety of defibrotide in addition to BSC vs BSC alone, including adverse event (AE) profile, serious adverse event (SAE) profile, laboratory abnormalities, and vital signs (including peri-infusional vital signs for subjects who receive defibrotide)
- To compare the overall safety of defibrotide in addition to BSC vs BSC alone by comparing the incidence of Grades 2, 3, and 4 acute GvHD by Days +30, +100, and +180 post-HSCT, and the incidence of chronic GvHD by Day +180 post-HSCT
- To compare graft failure and time to neutrophil and platelet engraftment

4.2.3 Exploratory Objectives

The exploratory objectives of this study are as follows:

- To compare the hospital resource utilization for subjects in the DP and BSC arms.
- To evaluate plasma concentration of potential predictive or prognostic VOD biomarkers (which may include, but will not be limited to vascular cell adhesion molecule 1 [VCAM1], von Willebrand factor [vWF], L-ficolin, plasminogen activator inhibitor [PAI-1], thrombomodulin, C-reactive protein [CRP], angiopoietin 2 [ANG2]) and/or GvHD biomarkers (which may include, but will not be limited to tumor necrosis factor receptor 1 [TNFR1], interleukin-1 receptor-like-1 [IL1RL1, also known as ST2], and regenerating islet-derived 3-alpha [REG3 α])
- To evaluate immunogenicity of defibrotide in subjects who receive defibrotide for treatment or prophylaxis

4.3 Study Endpoints

4.3.1 Primary Endpoint

The primary efficacy endpoint is VOD-free survival at Day +30 post-HSCT as adjudicated by the independent EPAC. An event for the primary efficacy endpoint is defined as a VOD diagnosis (as assessed by the EPAC) or death, whichever is earlier, up to and including Day +30 post-HSCT.

4.3.1.1 Primary Study Hypothesis

The primary efficacy endpoint is a time-to-event endpoint. The statistical hypothesis for the primary endpoint is as follows:

- Null hypothesis (H_0): There is no difference in VOD-free survival by Day +30 post-HSCT between the DP and the BSC arms.
- Alternative hypothesis (H_1): There is a difference in VOD-free survival by Day +30 post-HSCT in favor of the DP arm over the BSC arm.

Superiority will be assessed using data from the intent-to-treat (ITT) analysis set. The study is designed with both an interim and a final analysis. To maintain an overall significance level at 1-sided alpha of 0.025, the incremental alpha is specified at 1-sided 0.0005 for the interim analysis and 1-sided 0.0245 for final analysis (the corresponding nominal alpha is 1-sided 0.0005 for interim analysis and 1-sided 0.02498 for final analysis).

4.3.2 Secondary Endpoints

4.3.2.1 Key Secondary Endpoint

The key secondary efficacy endpoint is VOD-free survival by Day +100 post-HSCT as adjudicated by the independent EPAC.

4.3.2.2 Key Secondary Study Hypothesis

The key secondary efficacy endpoint is a time-to-event endpoint. The statistical hypothesis is as follows:

- Null hypothesis (H_0): There is no difference in VOD-free survival by Day +100 post-HSCT between the DP and the BSC arms.
- Alternative hypothesis (H_1): There is a difference in VOD-free survival by Day +100 post-HSCT in favor of DP arm over BSC arm.

Superiority will be assessed using data from the ITT analysis set. To control the study-wise type I error, a sequential testing strategy will begin with the test on primary efficacy endpoint. If that test is significant, the test on the key secondary efficacy endpoint will be conducted at 1-sided alpha = 0.025. This gate-keeping approach will keep the family-wise error rate at 1-sided 0.025 for the comparisons of the 2 treatment arms in the primary and the key secondary efficacy endpoint analyses.

4.3.2.3 Other Secondary Endpoints

Other secondary efficacy endpoints will be tested without multiplicity adjustments, and nominal p-values will be reported. Other secondary efficacy endpoints include the following:

- Incidence of VOD by Day +30 post-HSCT
- VOD-free survival by Day +180 post-HSCT
- NRM by Days +100 and +180 post-HSCT

- Incidence of VOD-associated MOD (ie, severe VOD) by Days +30 and +100 post-HSCT (in those subjects who develop VOD)
- Proportion of subjects who have resolution of VOD by Day +180 post-HSCT and time to resolution of VOD
- Incidence of VOD after Day +30 post-HSCT up to Days +100 and +180 post-HSCT
- Health-related quality of life using EQ-5D-5L (adults only), EQ-5D-Y (proxy version 1; pediatric subjects 4 to 7 years of age), and EQ-5D-Y (self-report version 1; pediatric subjects 8 to <16 years of age)
- Pharmacokinetics of defibrotide
- Safety of defibrotide in addition to BSC vs BSC alone, including AE profile, SAE profile, laboratory abnormalities, and vital signs
- Incidence of Grades 2, 3, and 4 acute GvHD by Days +30, +100, and +180 post-HSCT, and the incidence of chronic GvHD by Day +180 post-HSCT
- Graft failure and time to neutrophil and platelet engraftment

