### 9.8.3 Other Secondary Efficacy Endpoints and Analyses

Other secondary efficacy endpoints include the following:

- Incidence of VOD by Day +30 post-HSCT
- VOD-free survival by Day +180 post-HSCT
- NRM by Day +100 and by Day +180 post-HSCT
- Incidence of VOD-associated MOD (i.e., severe VOD) by Day +30 and by Day +100 post-HSCT (in those patients who develop VOD)
- Proportion of patients who have resolution of VOD by Day +180 post-HSCT and time to resolution of VOD
- Incidence of VOD after Day +30 post-HSCT, by Day +100, and by Day +180 post-HSCT

These secondary efficacy endpoints will be tested without multiplicity adjustments, and nominal p-values will be reported.

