### 9.8.3.4 **Incidence of Multi-Organ Dysfunction**

The proportion of patients who develop VOD-associated MOD (i.e., severe VOD), as defined in [Section 6.3.3.2](#), by Day +30 and Day +100 post-HSCT will be summarized and compared between the 2 treatment arms using a chi-square test.

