10.2.2 Other Secondary Efficacy Endpoints

These other secondary efficacy endpoints will be tested without multiplicity adjustments, and nominal p-values will be reported. The ITT Analysis Set will be used for these analyses.

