10.2.2.4 Incidence of VOD-associated MOD by Days +30 and +100 post-HSCT

VOD-associated MOD is defined for subjects as occurring if the investigator answers “Yes” to the question “Has the subject been diagnosed with VOD associated MOD?” in the eCRF. The number and proportion of subjects who develop VOD-associated MOD by Days +30 and +100 post-HSCT will be summarized and compared between the 2 treatment arms using a chi-square test.

The following summary will be provided:

- Summary of VOD-associated MOD

The following listing will be provided and will include the date of MOD and type of renal and pulmonary dysfunction:

- Listing of VOD-associated MOD

10.2.2.5 Resolution of VOD by Day +180 post-HSCT and Time to Resolution of VOD

Of those subjects who were diagnosed with VOD by Day +30 post-HSCT by the investigator, the proportion of subjects who have resolution of VOD by Day +180 post-HSCT will be summarized by treatment arm.

Time to resolution of VOD will be calculated as follows:

Time to resolution of VOD = [Date of VOD resolution] – [Date of VOD diagnosis by investigator]

If VOD does not resolve by Day +180 post-HSCT, the subject will be censored on the date of the Day +180 post-HSCT VOD resolution assessment. If the Day +180 post-HSCT VOD resolution assessment is missing, they will be censored on the date of the last VOD resolution assessment performed.

The following will be presented for VOD resolution by Day +180 post-HSCT:

- The number of subjects by treatment group who had an event and who were censored (either due to not having an event or for other reasons as described above).
- The p-value from a log rank test stratified by risk status and age group.
- The KM estimates of the NRM rate (%) with 95% CI.
- the KM estimate of median time to NRM in days (95% CI).
- The HR (95% CI) from a Cox proportional hazards regression model stratified by risk status and age group.
- A KM plot will be presented up to Day +180 post-HSCT for each treatment arm. The number of subjects at risk will be displayed at 10-day intervals.

The following summary will be provided:

- Analysis of VOD resolution by Day +180 post-HSCT

The following figure will be provided:

- Figure of VOD resolution by Day +180 post-HSCT

The following listing will be provided and will include whether or not VOD was resolved, the criteria met for resolution, and the date of resolution:

- Listing of VOD resolution

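### Severe VOD (VOD-associated MOD) is defined among subjects who develop VOD but assigned to the ITT set, and no section names the denominator of the tested proportion

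*SAP*

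**What the plan says.** **Endpoint wording.** SAP 4.3.2.3 lists "Incidence of VOD-associated MOD (ie, severe VOD) by Days +30 and +100 post-HSCT (in those subjects who develop VOD", and SAP 4.2.2 words the objective the same way. Protocol 9.8.3 has "Incidence of VOD-associated MOD (i.e., severe VOD) by Day +30 and by Day +100 post-HSCT (in those patients who develop VOD", matching the objective in Protocol 2.2. All four places tie the incidence to subjects with VOD.

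**Analysis wording.** SAP 6.2 makes ITT the primary set for every efficacy endpoint, and Protocol 9.4 agrees. SAP 10.2.2, which heads the other secondary efficacy analyses, adds: "The ITT Analysis Set will be used for these analyses". SAP 10.2.2.4 then states: "The number and proportion of subjects who develop VOD-associated MOD by Days +30 and +100 post-HSCT will be summarized and compared", using a chi-square test. Protocol 9.8.3.4 likewise tests "The proportion of patients who develop VOD-associated MOD (i.e., severe VOD". Neither analysis section names a denominator or repeats the restriction.

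**Source of the event.** SAP 10.2.2.4 takes MOD from an investigator yes/no item on the eCRF. VOD incidence by Day +30 (SAP 10.2.2.1) is EPAC-assessed.

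**The concern.** The two wordings describe two quantities. One is the probability, for a randomised subject, of developing severe VOD. The other is the probability that a VOD case is severe. Both can be tested by chi-square, and both could be reported under the same endpoint name.

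Only the first is a randomised comparison. VOD occurs after randomisation and is the event that prophylaxis is meant to prevent, so subjects who still develop it on defibrotide need not resemble those who develop it on best supportive care. A difference in severity between these groups, or its absence, mixes drug effect with selection. A nominal p-value there would look like randomised evidence without being so.

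The choice can also decide the message. A drug that prevents VOD without changing severity per case reduces severe VOD among all randomised subjects and shows nothing among VOD cases. A drug that prevents only the milder cases shows no effect among all randomised subjects and apparent harm among VOD cases.

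**Working it through.** The plan gives no figure for MOD, so there is none to reproduce for this endpoint. The design rates borrowed below are internally consistent: ln(0.86)/ln(0.72) = 0.459, the stated hazard ratio of 0.46. A two-look simulation with 360 completers and futility stopping gives 90.2% power and 68.1 events on average, against the stated 90% and 68.

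**Inputs from the documents**
- 200 subjects per arm (SAP 4.6).
- VOD or death by Day +30: 14% DP, 28% BSC (SAP 4.6). This is a composite, so it can only stand in for VOD.
- VOD alone by Day +30 in the earlier randomised paediatric trial: 12% v 20% (Protocol 1.2).
- All-cause mortality by Day +30: estimated at 5% to 10% (Protocol 1.5).

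**Assumptions**
- q, the share of VOD cases with MOD, is not given. I use 40%, with a range of 20% to 50%. The osteopetrosis series in Protocol 1.2 had 3 severe cases among 7 control VOD cases (43%), which is too few to fix a value.
- Tests are two-sided at 0.05, because the SAP promises only a nominal p-value.

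**Formulas.** With VOD probability p and arms D (DP) and B (BSC):
- all randomised: rate = p × q, so RR = (p_D × q_D)/(p_B × q_B)
- VOD cases only: rate = q, so RR = q_D/q_B

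If q_D = q_B, the first ratio reduces to p_D/p_B and the second to 1.

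**Equal shares, q = 40%**

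| VOD rates, DP v BSC | All randomised, DP v BSC | RR | Power | VOD-only RR |
|---|---|---|---|---|
| 12% v 20% | 4.8% v 8.0% | 0.60 | 26% (about 25% by simulation) | 1.00 |
| 14% v 28% (composite as stand-in) | 5.6% v 11.2% | 0.50 | 52% | 1.00 |

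For q from 20% to 50%, power runs from 15% to 31% in the first row and from 29% to 63% in the second. The ratios do not move. Removing 5 or 8 points of death from both arms of the composite leaves VOD at 9% v 23% or 6% v 20%, with all-randomised ratios of 0.39 and 0.30. The VOD-only ratio stays at 1.00.

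**The same events under both denominators.** Using the stand-in rates, there are 200 × 0.28 = 56 BSC and 200 × 0.14 = 28 DP cases. At q near 40% this gives 22 v 11 MOD events.
- All randomised: 22/200 v 11/200, p = 0.046.
- VOD only: 22/56 v 11/28, p = 1.00.

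**Only non-severe cases prevented.** With q = 30% in BSC, 0.30 × 56 = 16.8, or about 17 MOD events, and the same 17 in DP.
- All randomised: 17/200 v 17/200, 8.5% in each arm.
- VOD only: 17/56 = 30% in BSC v 17/28 = 61% in DP, p = 0.008 against the drug.

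**The case against.** The strongest reply is that the analysis text already settles the matter. ITT is assigned twice in the SAP. Where this part of the SAP wants a subset it says so: non-relapse mortality (10.2.2.3) is confined to malignant primary disease, and VOD resolution (10.2.2.5) to investigator-diagnosed VOD by Day +30. The MOD paragraph has no such limit. Protocol 6.3.3.3 defines this MOD as organ dysfunction in the presence of VOD, so the parenthetical may only describe who can have the event. The mock shells are held in a separate document (SAP Section 3) and may show the denominator.

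Much of this stands. A reader might infer that a VOD-only test is planned, or that two competing tests are. The documents do not support that: no analysis section specifies one, and the text leans the other way.

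What does not stand is that the question is closed. In Protocol 2.2 and SAP 4.2.2 the same parenthetical is attached to VOD resolution, where it does define the denominator. A programmer could fairly read it the same way for MOD, and nothing in the SAP rules that out.

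Two further inferences should be resisted. One is that severe VOD is what justifies the trial. Protocol 3.2 frames the hypothesis as reducing VOD incidence and cites MOD mortality only when describing clinical benefit. The other is that a halving of severe VOD is to be expected. That follows only if the composite rates stand in for VOD and the MOD share is equal in both arms.

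**Conclusion.** The endpoint definition and the analysis text are inconsistent, and the denominator of a tested proportion is left open. The all-randomised reading is the likelier intention and the better analysis. The literal endpoint reading would give a nominal p-value that randomisation does not protect.

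With equal MOD shares the contrast is an all-randomised ratio of 0.60 or 0.50, depending on which documented rates are used, against 1.0 among VOD cases. It does not depend on the size of the share, but the power figures do. The reversal to 30% v 61% is an illustration of what selection can do, not a forecast. It rests on the stand-in VOD rates, a 30% share in BSC and no prevention of severe cases.

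A reader might take this as a threat to the trial's conclusions. It is not: SAP 7.2 and 10.2.2 place the endpoint outside the gatekeeping with nominal p-values, so primary and key secondary inference are unaffected. The point is to have one defined, randomised comparison of severe VOD, fixed before the data are seen.

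**What to change.** 1. In SAP 10.2.2.4, state that the tested proportion at Days +30 and +100 has all randomised subjects in each arm as its denominator.
2. Remove the parenthetical from the MOD item in SAP 4.2.2 and 4.3.2.3.
3. If the share of VOD cases with MOD is wanted, show it as a descriptive row without a p-value. State whether VOD there is investigator- or EPAC-assessed: MOD comes from the investigator, so an EPAC denominator could leave out some MOD cases.
4. Check that the table shell agrees.

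The cost is a few words in the SAP, with no new data, and SAP Section 3 allows such decisions up to the database freeze. The SAP change is enough by itself. Protocol 2.2 and 9.8.3 carry the same parenthetical, but Protocol 11.6 requires a formal amendment with IRB/IEC approval for any change, so align them at the next amendment if there is one.

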4.3.3 Exploratory Endpoints

Exploratory endpoints include the following:

- Hospital resource utilization
- Evaluate plasma concentration of potential predictive or prognostic VOD biomarkers (which may include, but will not be limited to VCAM1, vWF, L-ficolin, PAI-1, thrombomodulin, CRP, ANG2) and/or GvHD biomarkers (which may include, but will not be limited to TNFR1, IL1RL1 (also known as ST2), and REG3 α)
- Evaluate immunogenicity of defibrotide in subjects who receive defibrotide for treatment or prophylaxis

4.4 Study Treatments

For subjects randomized to the DP arm, defibrotide solution is administered intravenously by study site personnel at a dose of 25 mg/kg/day, divided into 4 equal doses of 6.25 mg/kg/dose given as 2-hour infusions every 6 hours. Defibrotide administration is recommended for a minimum of 21 days beginning within 24 hours prior to the start of the conditioning regimen (2-4 doses of defibrotide should be administered within 24 hours prior to conditioning regimen) and ending no later than Day +30 post-HSCT. Subjects in this arm of the study will also receive standard of care therapy based on local institutional guidelines and subject need.

Subjects randomized to the BSC arm should receive standard of care therapy according to institutional guidelines and subject need. Best supportive care is intended to serve as study control for comparison with those subjects randomized to receive DP. Administration of BSC will begin on the first day of conditioning and continue until Day +30 post-HSCT or hospital discharge, whichever is sooner, or diagnosis of VOD, if applicable.

